**PROTOCOL TITLE**

Remote-delivered Mindfulness-Based Cognitive Therapy to Target Fear of Recurrence among SCAD Survivors

**FUNDING**

NIH

**VERSION DATE**

3/09/22

**SPECIFIC AIMS**

Concisely state the objectives of the study and the hypothesis being tested.

The proposed research study has the following objectives:

**Specific Aim 1:** To explore feasibility and acceptability of UpBeat-MBCT for SCAD survivors and make treatment refinements (2 sequential groups of approx. N=8 survivors/group).

Hypotheses: (1) The intervention will be feasible (enrollment, retention, attendance  $\geq 70\%$ ); and (2) acceptable (satisfaction ratings  $\geq 70\%$ , exit interview themes of satisfaction).

**Specific Aim 2:** To explore feasibility of the research procedures (pre-post intervention surveys, daily diaries, actigraphy use). Hypothesis: Each research procedure will be feasible ( $\geq 70\%$  completion).

**Specific Aim 3 (exploratory):** To explore changes in psychological and behavioral variables and their associations. **3a:** To explore changes in psychological variables. Hypothesis: Participants will report improvements in each UpBeat-MBCT mechanism (non-judgmental body awareness, attention regulation, cognitive de-centering, distress tolerance), FOR process (interoceptive bias, intolerance of uncertainty), and FOR outcome (FOR severity, cardiac anxiety). **3b:** To explore changes in behavioral variables. Hypothesis: Participants will report improvements in sleep and physical activity outcomes. **3c:** To explore associations between changes in psychological and behavioral variables. Hypothesis: Changes in psychological variables will be correlated with changes in behavioral variables.

**BACKGROUND AND SIGNIFICANCE**

Provide a brief paragraph summarizing prior experience important for understanding the proposed study and procedures.

Spontaneous coronary artery dissection (SCAD) is an important yet understudied cause of acute cardiac events, involving the sudden separation of layers of a coronary artery wall, leading to obstructed blood flow. SCAD primarily affects healthy women with no cardiovascular risk factors, accounting for up to 40% of cardiac events in young women.

The 10-year recurrence rate is 30%, but SCAD recurrence cannot be predicted. Given the unpredictable onset and disease course, SCAD survivors commonly struggle with high fear of recurrence (FOR). Critically, elevated FOR is associated with poor health behaviors including poor sleep and physical inactivity, which further increase the risk of future cardiac events. A scientific statement from the American Heart Association identified a need for interventions to improve outcomes after SCAD, but there have been no interventions developed to improve FOR or health behaviors in SCAD survivors.

Mindfulness-Based Cognitive Therapy (MBCT) has the potential to improve FOR and health behaviors in SCAD survivors. Evidence supports the efficacy of MBCT to improve FOR, sleep outcomes, and physical activity, in other patient populations. MBCT is an 8-session group intervention that combines cognitive behavioral therapy with mindfulness meditation to teach non-judgmental awareness and self-regulation of attention toward the present moment. Our published empirical model explicates how MBCT can reduce FOR via increases in four mechanisms of action (non-judgmental body awareness, attention regulation, cognitive de-centering, distress tolerance) that directly target reductions in two key FOR processes (interoceptive bias, intolerance of uncertainty), resulting in improvements in FOR severity and, subsequently, health behaviors.

Through the PI's current NIH K23 award, our team has already adapted MBCT to target the needs of acute cardiac event survivors. The adapted intervention (UpBeat-MBCT), was developed through qualitative interviews with 22 cardiac event survivors, primarily men who survived acute coronary syndrome (Insight Protocol # 2018P001000). Results revealed a multitude of quality of life concerns including FOR, sleep problems, and physical inactivity. We adapted MBCT to target these concerns and be appropriate for group videoconferencing delivery (Insight Protocol #2020P000045). Given the patient-informed adaptations and MBCT mechanisms of action, UpBeat-MBCT is hypothesized to be feasible, acceptable, and improve FOR and, thereby, health behaviors, for SCAD survivors. Given the unique sociodemographic and medical characteristics of SCAD survivors, there may be ways to further target UpBeat-MBCT to optimize relevance and benefits for this unique population.

This study proposes to adapt the UpBeat-MBCT intervention for SCAD survivors and test the feasibility and acceptability of the intervention, delivered via group videoconferencing in an open pilot trial. We will explore changes in psychological and behavioral variables. This innovative project will be the first to explore MBCT for SCAD survivors. It will generate knowledge about e-health technologies and congruent research methods to apply to other mind-body interventions and patient populations.

## **RESEARCH DESIGN AND METHODS**

Briefly describe study design and anticipated enrollment, i.e., number of subjects to be enrolled by researchers study-wide and by Mass General Brigham researchers. Provide a brief summary of the eligibility criteria (for example, age range, gender, medical condition). Include any local site restrictions, for example, "Enrollment at Mass General Brigham will be limited to adults although the sponsor's protocol is open to both children and adults."

The current study will employ an open pilot trial to determine the initial feasibility and

acceptability of a targeted, virtual UpBeat-MBCT intervention for SCAD survivors. We plan to enroll approximately N=20 participants (approx. n=8 survivors/group, accounting for 20% anticipated lost to follow-up). The UpBeat-MBCT intervention will involve 8 MBCT sessions (approximately 1.5 hours each) delivered via synchronous group videoconference, which combines cognitive-behavioral therapy, mindfulness meditation, and cardiac health behavior promotion. During each session, participants will be taught how to use evidence-based mindfulness skills to reduce fear of recurrence and promote positive health behaviors (and physical activity). We will hold two intervention cohort groups that will be run sequentially. Participants in the intervention will be asked to complete a full survey battery of the measures before and after the intervention, and wear an actigraphy device (e.g., to measure physical activity and sleep patterns) for 7 consecutive days within the 1-2 weeks before and after the intervention. In addition, participants will be asked to complete a daily diary of abbreviated measures for 1-2 weeks before and after the intervention. Upon completion of the intervention, participants will complete an audio- or video-recorded exit interview (approx. 45-60 minutes).

**Inclusion criteria:**

1. Age  $\geq$  18
2. Cardiologist-confirmed diagnosis of SCAD in the past 3-18 months
3. Internet access (via computer or mobile device)
4. English-speaking and reading

**Exclusion criteria:**

1. Terminal illness with life expectancy  $<$ 1 year
2. Severe mental illness requiring urgent psychiatric intervention or past-year psychiatric hospitalization
3. Significant cognitive impairment preventing informed consent
4. Deemed unable to complete research procedures
5. Unavailable for intervention sessions (e.g., schedule conflicts)

There are no exclusion criteria with respect to ethnicity or socioeconomic status.

Briefly describe study procedures. Include any local site restrictions, for example, "Subjects enrolled at Mass General Brigham will not participate in the pharmacokinetic portion of the study." Describe study endpoints.

**Participant communication:**

Participants will be asked to specify their preferred contact modalities following informed consent. Study staff will attempt to engage in contact via phone, paper mail, and/or email to schedule group sessions, send study materials and reminders, and send questionnaire batteries and daily diary surveys. At minimum, participants will be asked to provide a home address, telephone number, and email address to allow for contact and delivery of study materials (e.g., intervention materials, actigraphy device, gift cards, etc.). Participants will be made aware of MGB policies regarding email per the information below:

Email: Participants will be given the option to communicate (e.g., receive reminders, schedule, etc.) with study staff by email. If the participant chooses email as their preferred method of communication, study staff will explain the encrypted, send secure default feature of emails sent within the MGB Healthcare network. Patients will receive the following information:

"The MGB standard is to send email securely. This requires you to initially set up and activate an account with a password. You can then use the password to access secure

emails sent to you from MGB. If you prefer, we can send you “unencrypted” email that is not secure and could result in the unauthorized use or disclosure of your information. If you want to receive communications by unencrypted email despite these risks, MGB will not be held responsible. Your preference to receive unencrypted email will apply to research studies for emails sent to you from research staff in this study. If you wish to communicate with other research staff at MGB regarding additional studies, your preference will have to be documented with each research group.”

**Adapted MBCT intervention:**

UpBeat-MBCT represents our recent adaptation of the evidence-based MBCT protocol, targeted to the needs of acute cardiac event survivors based on the study PI’s K23 qualitative research (IRB Protocol Number 2018P001000) and open pilot trial in patients after acute coronary syndrome (IRB Protocol Number 2021P000544). It is a virtual 8-week group intervention (approx. 90-minute weekly sessions) that combines cognitive-behavioral therapy, mindfulness meditation, and cardiac health behavior promotion. There is 15-20 minutes of daily mindfulness practice between sessions. Participants are provided an optional home practice record form that they can use to keep track of their practice between sessions if they would like. The UpBeat-MBCT will be tested in the first intervention group, then refined to further target the intervention to SCAD survivors, creating SCAD-MBCT for testing in the second group.

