**Measured Outcomes:**

The primary outcomes are feasibility and acceptability of the intervention and research procedures. The exploratory outcomes are changes in psychological and behavioral variables, measured via pre-post intervention surveys, and daily diaries and actigraphy each day for 1-2

weeks before and after the intervention. Daily diaries will include psychological variables and self-reported physical activity (collected at night) and sleep outcomes (collected at morning). Covariates will be extracted from the medical record, including date of SCAD event, pregnancy-associated SCAD, medical and psychiatric comorbidities, cardiac rehab attendance, and hospital readmissions. Please refer to tables 1 and 2 below for details of feasibility and acceptability outcomes (Table 1) and exploratory outcomes (Table 2).

Table 1. PRIMARY OUTCOMES (Aims 1 and 2)	
Feasibility	
Enrollment	≥70% of eligible enroll; <20% ineligible due to each criterion; reasons for ineligibility; reasons for refusal; characteristics of refusers
Retention	≤20% participant attrition
Intervention components	≥70% session attendance; fidelity score ≥70%; ≤20% of sessions missed due to videoconference problems; ≤20% connections dropped during session; number (M≤2.0) and types of videoconference problems
Surveys	≥70% pre-intervention and post-intervention surveys completed; ≥70% daily diaries completed for 7 consecutive days; ≤20% missing data on daily diaries
Actigraphy	≥70% completed 7 consecutive days
Acceptability	
Intervention components	Program satisfaction (M≥7.0), ≥70% plan to use the skills, ≥70% would recommend the program to others ( post-survey ); likes, dislikes, suggestions for program improvement ( exit interview )
Surveys	Ease of survey completion (1=not at all, 10=extremely M≥7.0); level of interference (1=not at all, 10=extremely M≤2.0; post-survey ); experiences, challenges, suggestions for improvement ( exit interview )
Actigraphy	Ease of actigraphy completion (1=not at all, 10=extremely M≥7.0; post-survey ); experiences, challenges, suggestions ( exit interview )

Table 2. EXPLORATORY OUTCOMES (Aim 3)		
Psychological Variables	Measurement	Model Component
Non-judgmental body awareness	Multidimensional Assessment of Interoceptive Awareness	Intervention mechanism
Attention regulation	Cognitive Affective Mindfulness Scale-Revised	Intervention mechanism

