## Analysis Plan

For Aim 1 and Aim 2 will calculate frequencies and proportions and means and standard deviations (or medians and interquartile ranges if variables are non-normal) to assess feasibility and acceptability outcomes. T-tests or chi-square will be used to compare eligible patients who did and did not enroll, and those who enrolled and dropped out, on demographic and clinical variables. Exit interviews will be audio recorded, transcribed, and iteratively analyzed using

thematic content analysis in NVivo 11. Transcripts will be reviewed by two members of the study team to identify themes and develop a coding framework. Discrepancies in coding will then be resolved through discussion.

For Aim 3, we will examine frequency distributions for each exploratory outcome at each timepoint and use non-parametric tests if needed. We plan to use linear mixed effects models with repeated measures and an unstructured covariance matrix to assess changes over time for each psychological and behavioral variable (separate dependent variables). The predictor variables will be time (fixed effect: up to 16 levels across pre-post intervention surveys and daily diaries or actigraphy) and covariates relevant for each dependent variable (random effects). If there are any time effects, we will conduct follow up analyses to determine if those effects show a change over the course of the intervention period in the expected direction. We will create change scores (post-intervention survey minus pre-intervention survey) and explore correlations of changes in psychological variables with changes in behavioral variables. Missing data will be imputed using maximum likelihood estimation and, as a sensitivity analysis, the last observation carried forward. Given the exploratory nature of the proposed pilot study, we will focus the interpretation of Aim 3 analyses on effect sizes (Cohen's d) rather than statistical significance to assess potential signals for intervention effects.

For studies involving treatment or diagnosis, provide information about standard of care at Mass General Brigham (e.g., BWH, MGH) and indicate how the study procedures differ from standard care. Provide information on available alternative treatments, procedures, or methods of diagnosis.

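### Do the Aim 1 benchmarks describe one program or two, given that the second group receives a version with a new name?

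*Combined protocol and SAP*

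**What the plan says.** Specific Aims, Aim 1: "To explore feasibility and acceptability of UpBeat-MBCT for SCAD survivors and make treatment refinements (2 sequential groups of approx. N=8 survivors/group"). Its first hypothesis begins "The intervention will be feasible (enrollment, retention, attendance", with 70% as the threshold.

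Background and Significance states the expectation by program name: "UpBeat-MBCT is hypothesized to be feasible, acceptable, and improve FOR and, thereby, health behaviors, for SCAD survivors". The same section goes on to say that there may be room to target the program further to this population, and that the study will adapt it for SCAD survivors and test the result.

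Research Design and Methods describes the objective as "acceptability of a targeted, virtual UpBeat-MBCT intervention for SCAD survivors. We plan to enroll approximately N=20 participants", in two cohorts run one after the other, with about 8 per group after 20% loss to follow-up.

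The section on the adapted MBCT intervention is the only place with a second name: "The UpBeat-MBCT will be tested in the first intervention group, then refined to further target the intervention to SCAD survivors, creating SCAD-MBCT for testing". The refined version is meant for the later cohort.

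Table 1 under Measured Outcomes has one set of benchmarks, for example "≥70% plan to use the skills, ≥70% would recommend the program to others". For Aims 1 and 2 the Analysis Plan "will calculate frequencies and proportions and means and standard deviations", with no split by group.

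**The concern.** Feasibility and acceptability are the primary outcomes, and most carry a numeric threshold that will be reported as met or not met. Such a statement needs a defined subject. Three sections name UpBeat-MBCT. A fourth gives that name to the first group's program and another name to the second's. Taken literally, Aim 1 would then concern the first group only, and no aim, hypothesis or benchmark would concern SCAD-MBCT at all.

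The denominator would change too: about 20 enrolled and 16 completers on one reading, about 10 and 8 on the other. The same data could pass a threshold on one reading and miss it on the other. With nothing written down, the choice could be made after the results are known.

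**Working it through.** **Planned size.** Two groups of about 8 completers give 2 × 8 = 16. With 20% loss, 16/(1 − 0.20) = 20 enrolled, or 8/0.80 = 10 per group. This reproduces the stated enrollment of about 20, so Aim 1 (8 per group) and the design summary (20 in all) agree.

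**What the passages say together.**
- Aim 1 has one object (UpBeat-MBCT), one activity besides testing it (refining it) and one sample (both groups), all in a single sentence.
- The background announces further targeting and adaptation as part of this study, then speaks of testing one intervention.
- The design summary already calls the program targeted.
- The intervention section says when the refinement happens and what the refined version is called. It says nothing about how a benchmark is scored.
- Table 1 and the Analysis Plan contain one set of benchmarks and one set of summaries. The ordinary reading is all participants.

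No passage calls for a verdict on the second group alone. If the program names were applied strictly to Aim 1, the alternative to pooling would be the first group, since that is where the name UpBeat-MBCT applies.

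**How often a single group would disagree with the total.** The documents give no expected rates, so the rates here are assumptions. Take a per-person 70% benchmark with independent responses.
- 16 completers: 0.70 × 16 = 11.2, so at least 12. One group of 8: 0.70 × 8 = 5.6, so at least 6.
- 20 enrolled: at least 14. One group of 10: at least 7.
- P(disagree) = P(total passes, group fails) + P(total fails, group passes), from binomial counts.

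| True rate, same in both groups | 8 per group | 10 per group |
|---|---|---|
| 70% | 0.073 + 0.175 = 0.247 (terms rounded) | 0.228 |
| 80% | 0.082 + 0.080 = 0.162 | 0.106 |
| 90% | 0.029 + 0.008 = 0.037 | 0.013 |

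With equal rates the two groups are exchangeable, so these figures hold for either group and for any arbitrary half of the participants. They measure the instability of a half sample and are not caused by the naming.

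**What by-group figures could show.** Exact (Clopper-Pearson) 95% intervals:
- 12/16: 48% to 93%
- 6/8: 35% to 97%
- 8/8: 63% to 100%

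Even a perfect result in one group of 8 would not exclude a true rate below 70%. Version also coincides with cohort and calendar period, so a difference between groups could not be credited to the refinement.

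**The case for a change.** The strongest case for a change is that a pooled pass can hide a poor result for the refined version, which is presumably the one to be carried forward. If all 10 in the first group meet a criterion, the total reaches 14 of 20 with only 14 − 10 = 4 of 10 in the second. With 8 per group it reaches 12 of 16 with 12 − 8 = 4 of 8. Under assumed true rates of 90% in the first group and 50% in the second, at 10 per group, the total passes with probability 0.61; in 0.44 it passes while the second group misses 70%. A sentence on pooling and some extra table columns would cost almost nothing.

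The arithmetic stands, and so does the observation that the pooling convention is not written down. The large figure, however, needs the refinement to make the program much worse. At 80% in both groups the corresponding probability is 0.07. A marked fall would also be hard to miss. Every participant is asked for an exit interview covering likes, dislikes and suggestions, session recordings are labelled by group number, and group membership is known for everyone. The split can be shown at reporting without amending the plan. The low cost is a reason to welcome the split, but it does not make the plan unsound without it.

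**Conclusion.** No change follows. The passages fit together as one program refined between two cohorts, which is what Aim 1 sets out to do, and the second name labels the later stage. What is missing is a stated convention for pooling. An analyst would fill it in the obvious way: one overall figure per benchmark across both groups, described as covering both versions. That is sound for a descriptive open pilot in which the documents attach no go/no-go rule to the benchmarks.

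The disagreement probabilities (0.25 to 0.04 at 8 per group and 0.23 to 0.01 at 10, for assumed common rates of 70% to 90%) do not measure harm from the wording, because any half of the sample would show them. No stated figure is wrong. Uniform program names, or descriptive by-group columns in the report, would be a courtesy to readers and would alter no analysis or conclusion.

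This rests on reading Table 1 and the Analysis Plan as applying to all participants, which is their natural sense. It would need another look if a decision rule were later tied to the refined version alone.

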**Intervention delivery:**

We will deliver the intervention using Zoom or a HIPPA compliant video-conferencing platform approved by MGB for use in research virtual visits. Zoom is a secure, HIPPA compliant video-conferencing software amenable to study procedures, which we have used successfully in prior studies to deliver mindfulness interventions to other patient populations (IRB Protocol Number 2020P000045). Participants will be informed during consent procedures that the videoconferencing system uses a secure, HIPPA-compliant software program. We will explain that although we will do our best to ensure confidentiality on our end and ask group members to not share information outside of the group, we cannot guarantee that other group members will not share the content of the group. Participants will be advised to wear headphones and sit in a quiet place to protect their own and other group members’ privacy.

Zoom is routinely used at MGB institutions and there is an enterprise license structure and BAA that is in place and managed by my team. There is no end-user license agreement for individuals to sign. Licenses are assigned by my team and users are sent an email with instructions/links on how to use the system. Only meeting hosts need to install the app. Zoom is a cloud-based solution, so participants need only click on the meeting link in the invitation.

Participants will receive training from study staff prior to the start of the intervention regarding the proper use of the video-conferencing software. Study staff will take the necessary steps to ensure that the participant is trained in using the videoconferencing software, and the RA will be available during intervention sessions to assist with any challenges. We will train participants in the videoconferencing program using the training methods ACS patients have asked for and which we have used successfully in our prior studies (e.g., instructional handouts, training sessions with an RA; IRB Protocol Number 2020P000045).

Intervention fidelity. The intervention will be delivered by the PI, who is a licensed clinical psychologist highly trained in the MBCT protocol, and who developed the adapted UpBeat-MBCT protocol in prior studies. All sessions will be audio-visually recorded using the capabilities of the videoconferencing system, after describing this during informed consent and reminding the participants that we will do so at the start of the first session. The PI and/or another trained study staff clinician will review session recordings and complete a validated MBCT fidelity checklist measure (MBCT-AS; included in the IRB submission). We will use the session

recordings and fidelity assessment to ensure that the intervention is being delivered as intended and are in adherence to the MBCT protocol. Video recording of MBCT sessions is necessary for ensuring that the intervention is delivered properly. Intervention fidelity is a critical aspect of behavioral intervention research, and video recording of intervention sessions allows for assessment of interventionist body language, non-verbal communication, and connection with participants, which cannot be obtained from audio alone, and are critical to the delivery of the MBCT intervention in particular. We are using video recording of MBCT sessions in our other NIH-funded trials of MBCT (IRB# 2020P000045; 2021P000544). Regarding the exit interview, we revised the protocol summary to state that we will only store audio recordings. We will conduct the interviews via Zoom but will ask participants to turn their camera off and/or only save the audio file of the Zoom recording.

Secure storage of recordings. Audio-video files will be labeled with the intervention group number, session number, and date. Contact information and personal identifying information about the participants will be held in separate, password-protected files on a secure Partner's network. All audio-video files will be stored on a password-protected drive on a secure MGB network immediately following each intervention session and will be destroyed 7 years following the completion of the study.

